3.2 Analysis Populations

3.2.1 *Intent-to-Treat (ITT) Population*

The Intent-to-Treat (ITT) Population will include all participants randomized into the study. Treatment classification will be based on the randomized treatment.

3.2.2 *Modified Intent-to-Treat (mITT) Population*

The Modified ITT (mITT) Population will include all participants in the ITT Population who receive at least 1 dose of any study drug and have a Baseline value for the LDL-C assessment. Any efficacy measurement obtained during the Safety Follow-up Visit after a participant

permanently discontinues the study drug or after a participant receives an excluded medication and/or procedure will be removed from the mITT analysis. Treatment classification will be based on the randomized treatment. The mITT Population will be used for the primary analysis of all efficacy endpoints.

3.2.3 Modified Intent-to-Treat (mITT) On-Treatment Population

The mITT On-Treatment Population will include all randomized participants who have a Baseline value for LDL-C assessment, have a Day 56 value for the LDL-C assessment, and plasma obicetrapib concentration at Day 56 is >100 ng/mL. Treatment classification will be based on the randomized treatment.

Rationale: <100 ng/mL is more than three standard deviations from the mean plasma obicetrapib concentration observed in both the ROSE (TA-8995-201) and TULIP (TA-8995-03) [with a very similar patient population compared to ROSE2 (TA-8995-202)] at respectively week 4 and week 12. In addition, in none of the previous conducted studies (3 clinical studies and 2 Phase 1 PK / PD studies the minimal observed obicetrapib concentration for C_{max} was below 100 ng/mL.

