8.7 Clinical Laboratory Evaluations

Blood for chemistry and hematology will be obtained as indicated in Appendix A and sent to a central laboratory for analysis. See Appendix B for a complete list of analytes. Blood samples for chemistry and hematology must be obtained under fasting conditions (i.e., after the participant has fasted for approximately 8 hours). For the purposes of this study, fasting will be defined as nothing by mouth except water and any essential medications. If a participant is not fasting, the Investigator should reschedule the visit as soon as possible. Estimated glomerular filtration rate will be calculated using the Chronic Kidney Disease Epidemiology Collaboration equation.⁶ At the Screening Visit only, the chemistry panel will include HbA1c.

A urine pregnancy test will be performed for women of childbearing potential at the Screening Visit (Visit 1) prior to their participation in the study and at the Safety Follow-Up Visit (Visit 6), and the Early Termination Visit, if appropriate.

An FSH test will be performed at the Screening Visit prior to participation in the study in women <55 years of age for whom it has been ≥1 year since their last menstrual period to confirm a postmenopausal state.

Blood samples for PK assessment will be collected as indicated in Appendix A. On Day 1 (Visit 2), a PK sample will be collected pre-dose. The subsequent post-dose PK samples should be collected once at approximately the same time at each visit.

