Coronavirus Disease 2019 Contingency Measures

In cases of COVID-19 limitations, it is the Investigator's responsibility to assure the safety of participants. If investigators need to implement contingency measures, the investigators will communicate with the Sponsor and discuss the best practice with the sponsor. In the absence of a COVID-19 impact, it is expected that Investigators and participants follow the protocol requirements as set forth.

2.2.2 *Randomization and Blinding*

Participants who meet all eligibility criteria will be randomized into the study. Participants will be randomized in a 1:1:1:1 ratio to the 2.5 mg obicetrapib, 5 mg obicetrapib, 10 mg obicetrapib, or placebo treatment groups. At randomization, participants will be stratified according to their Screening Visit (Visit 1) LDL-C level (≥ 100 or < 100 mg/dL). An automated interactive response technology (IRT) system will be used to assign the participant to 1 of the 4 treatment groups, and visits will be registered in the IRT for Screening and Visits 1 through 5 as well as Early Termination, if applicable.

Participants, Investigators, the CRO, and the Sponsor will be blinded to all lipid results from Day 1 (Visit 2) for the first participant and continuing to database lock in order to protect blinding to treatment assignment.

2.2.3 *Study Drug*

The study drugs to be used in this study include the following:

- 2.5 mg obicetrapib tablet;
- 5 mg obicetrapib tablet;
- 10 mg obicetrapib tablet; and
- Matching placebo tablet.

The study drugs listed above will be packaged to provide doses of 2.5 mg, 5 mg, 10 mg obicetrapib, or placebo only. Placebo tablets will be visually identical. Participants will be randomized to receive 1 of the 3 doses of obicetrapib or placebo only. One tablet of study drug will be administered by the participant orally once daily from Day 1 (Visit 2) to Day 56 (Visit 5) at approximately the same time each morning.

2.2.4 *Sample Size Determination*

A sample size of at least 100 evaluable participants (i.e., 25 participants per treatment group) will provide $>90\%$ power to detect a 30% difference in LDL-C reduction at Day 56 (standard deviation (SD) of 25%) for each of the obicetrapib groups compared to the placebo group at a 2-sided significance level of 0.05.

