3.4.1 Primary Efficacy Endpoint

Primary Analysis

The primary efficacy endpoint is the percent change from Day 1 to Day 56 in LDL-C (as determined by approach 1) for each obicetrapib group compared to the placebo group. The percent change will be calculated from Day 1 (Baseline) to each measurement taken at Day 14, Day 28, and Day 56.

The mean percent change from Day 1 to Day 56 in LDL-C for each treatment is defined mathematically as μ_j , where j stands for jth treatment (j=0,1,2,3) and the subscripts 0, 1, 2, and 3 refer to the placebo, Obicetrapib 10 mg, 5 mg, and 2.5 mg group, respectively. The hypotheses

testing to the difference in the mean percent change in LDL-C from Day 1 to Day 56 between the j^{th} obicetrapib group and the placebo group is then defined statistically as following:

$$H_0: \mu_j - \mu_0 = 0, H_1: \mu_j - \mu_0 \neq 0, \text{ where } j = 1, 2, 3$$

The primary efficacy analysis of the percent change from Day 1 to Day 56 in LDL-C will be performed using a mixed model for repeated measure (MMRM) approach. The analysis will include fixed effects for treatment, visit, and treatment-by-visit interaction, along with a covariate of the Baseline value as a continuous covariate. It is to note that randomization was stratified by categories of LDL-C value (≥ 100 or < 100 mg/dL) only to ensure similar distribution of LDL-C values across all treatment. However, the MMRM model will include the original scale of the LDL-C value as a continuous covariate, not categorical.

The Restricted Maximum Likelihood estimation approach will be used with an unstructured covariance matrix. The least squares means, standard errors, and 2-sided 95% confidence intervals for each treatment group and for the pairwise comparisons of each dose of obicetrapib to the placebo group will be provided. The least squares means for the pairwise comparison and its standard error will be used for the hypothesis testing. The ratio of estimate to standard error will be approximately t distributed. The null hypothesis of no treatment effect will be rejected if the p-value, the probability of obtaining the observed or more extreme value of t statistic under the null hypothesis, is less than or equal to 0.05.

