In order to maintain the overall alpha level on the primary endpoint, the hypothesis testing will be performed sequentially at the 2-sided alpha=0.05 significance level. The first comparison will be the 10 mg obicetrapib group versus placebo; if significant, comparison of the 5 mg obicetrapib group versus placebo will be performed, followed by the 2.5 mg obicetrapib group versus placebo. Hypothesis testing will proceed in this hierarchical step-down fashion until a comparison is not significant. At that point, all remaining sequential tests will be deemed not significant.

The MMRM approach will include all available assessments of percent change in LDL-C from Baseline to Day 14, Day 28, and Day 56. The model assumes the data are missing at random (MAR). If any data are missing, the model will use all information from the other time points as well as Baseline covariate values to estimate the mean treatment difference at the given time point. No imputation of missing data will be performed for the primary efficacy endpoint analysis.

In order to address the effect of intercurrent events, "While-on-Treatment Strategies" will be employed¹. For participants who are withdrawn from the study because of the use of an excluded medication and/or procedure, data occurring after the intercurrent event of excluded medications use will be excluded from the primary analysis. For participants who are withdrawn from the trial, data occurring after the intercurrent event of failure to adhere to treatment dosing will be excluded from the primary analysis. Failure to adhere to treatment dosing will be defined as study drug compliance <75% at the time of study withdrawal.

The MMRM analysis will be implemented using SAS[®] Proc Mixed. Example SAS code can be found below:

Note:

USUBJID = unique subject identifier

TREATMENT = 0 (Placebo), 1 (2.5 mg obicetrapib), 2 (5 mg obicetrapib), 3 (10 mg obicetrapib)

VISIT = Visit

BASE = Baseline value

PCHG = Percent change from Baseline

proc mixed;

class USUBJID TREATMENT VISIT;

model PCHG = TREATMENT BASE VISIT TREATMENT*VISIT / solution cl;

repeated VISIT / TYPE=UN sub=USUBJID;

lsmeans VISIT*TREATMENT / cl diffs;

run;

Values, changes from Baseline, and percent change from Baseline of LDL-C will be summarized using descriptive statistics at scheduled visits and Baseline by treatment group.

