Counts and percentages of participants will be summarized by treatment for each type of data pattern. There will be 16 data patterns for four time points (Baseline, Day 14, Day 28 and Day 56) each having two possible outcomes (LDL-C data reported or missing).

Waterfall plot of percent change in LDL-C from Baseline to each scheduled visit will be created. Line plot of the mean (+/- 2 * SE) and the median (and IQR) percent change in LDL-C from Baseline to each scheduled visit will be created. Figures will be created for LDL-C values collected using two approaches described above.

The main analyses for the primary efficacy endpoint will be repeated for the ITT Population, the mITT On-Treatment Population, and PP Population.

Sensitivity Analyses

Three sensitivity analyses will be performed for the primary efficacy endpoint:

1. MMRM with imputation
2. Analysis covariance (ANCOVA)
3. ANCOVA using LDL-C by PUC

All sensitivity analyses will be conducted on the mITT Population.

Sensitivity Analysis 1

The first sensitivity analysis will be performed in two steps. In the first step, missing data will be assumed missing not at random (MNAR). Missing data at Days 14, 28 and 56 will be imputed using multiple imputation methodology in two steps. Initially, 25 data sets will be imputed for non-monotone missing values in the original dataset. In the second step the remaining monotone missing values in the 25 data sets will be imputed based on the observations in the Placebo group. Upon completion of the trial, if the percentage of cases with incomplete data is larger than initially anticipated then the number of imputations will be increased for the final analysis.

The variables for the imputation model will consist of LDL-C values from Baseline and Days 14, 28 and 56. For each imputation dataset, the percent change from Baseline to Day 56 will be analyzed using the MMRM model described for the primary analysis. The results from these 25 analyses will be combined using Rubin's method to construct the treatment estimates using the parameter estimates and associated standard errors. Similarly, the difference of the adjusted

treatment means (the three doses of obicetrapib therapy – Placebo) will be presented with the associated standard error and 95% confidence interval. Randomly chosen seed numbers will be selected for the analysis and will be retained.

Example SAS code to create a dataset for non-monotone missing values is shown below:

```
*****
```

Note:

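### The mITT On-Treatment Population requires obicetrapib above 100 ng/mL of every randomized participant, so it excludes the placebo arm against which each dose is to be compared

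*SAP*

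**What the plan says.** SAP 3.2.3 defines the set by conditions that must all be met. It starts from the whole randomized sample: "The mITT On-Treatment Population will include all randomized participants who have a Baseline value for LDL-C assessment". The remaining conditions are that participants "have a Day 56 value for the LDL-C assessment, and plasma obicetrapib concentration at Day 56 is >100 ng/mL". Arm membership then follows allocation: "Treatment classification will be based on the randomized treatment".

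On the control arm, SAP 2.2.3 says: "Participants will be randomized to receive 1 of the 3 doses of obicetrapib or placebo only".

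On use of the set, SAP 3.4.1 says: "The main analyses for the primary efficacy endpoint will be repeated for the ITT Population, the mITT On-Treatment Population, and PP Population". The main analysis reports least squares means for each group, and estimates with confidence intervals "for the pairwise comparisons of each dose of obicetrapib to the placebo group will be provided". The example code lists placebo as treatment level 0 and requests the differences through "lsmeans VISIT*TREATMENT / cl diffs".

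The set appears again in SAP 3.3.4 (baseline tables), SAP 3.4 (supportive analyses) and SAP 5 (changes from the protocol). None of these mentions placebo. The protocol does not define the set.

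**The concern.** A minimum drug concentration is a way to pick out participants who took active drug. Applied to everyone, it removes the arm that has no active drug. The repeat in this population is meant to show the effect of each dose against placebo among participants with confirmed exposure, and without a placebo arm it cannot do so.

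Because classification is by randomized treatment, there is one way for the placebo arm not to be empty: a participant randomized to placebo takes obicetrapib and exceeds 100 ng/mL. The software would then return contrasts, but the control would be a person exposed to the drug under test. That is harder to notice than an empty column.

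Adding this population is one of only two changes from the protocol listed in SAP 5, so it was put there deliberately to support the primary endpoint.

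**Working it through.** **Inputs**
- Allocation 1:1:1:1; 25 evaluable per group, 100 in total; SD 25%; difference 30%; two-sided 0.05; power above 90%; 7% dropout; 108 randomized, 27 per group (SAP 2.2.2 and 2.2.4).
- Membership rule: SAP 3.2.3. Contrasts: SAP 3.4.1.
- Inference, not a measured value in the documents: a participant who takes only placebo has no obicetrapib above 100 ng/mL.

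**The plan's own figures reproduce**
- SE of a difference = 25 × √(1/25 + 1/25) = 7.07. Normal-approximation power = Φ(30/7.07 − 1.96) = Φ(2.28) = 98.9%; with the noncentral t it is 98.6%. Both agree with the stated power above 90%.
- Enrollment: 100/0.93 = 107.5, rounded up to 108; 25/0.93 = 26.9, rounded up to 27.

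The sample size is not in dispute.

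**Who qualifies under SAP 3.2.3 as written**

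| Arm | Evaluable | Can meet the >100 ng/mL condition |
|---|---|---|
| Each obicetrapib dose | 25 | Yes; at most 25 (the documents give no rate at or below the threshold) |
| Placebo, dosed as assigned | 25 | No; 0 |

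The share of the trial removed is 25/100 = 27/108 = 25%, all of it the control arm.

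**What the repeated model can estimate at Day 56**

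The plan intends 3 contrasts, one per dose against placebo. A rank check of the Day 56 design (intercept, four treatment levels, Baseline LDL-C), with 25 per obicetrapib arm, gives:
- placebo n = 0: 0 of 3 contrasts estimable. The example code would return only the C(3,2) = 3 differences between obicetrapib doses, none of which is an intended contrast;
- placebo n = 1: 3 of 3 computable;
- placebo n = 25: 3 of 3 estimable.

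**If one placebo participant took obicetrapib in error and qualified (hypothetical)**

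Assume SD 25 and all 25 in each obicetrapib arm above the threshold. Residual degrees of freedom are participants minus 5 fitted parameters (4 arms and Baseline).
- 25 v 1: SE = 25 × √(1/25 + 1/1) = 25.5; 76 − 5 = 71 df; 95% CI half-width 50.8 points.
- 25 v 25: SE = 7.07; 100 − 5 = 95 df; half-width 14.0 points.

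The lost precision is secondary. The estimate would be invalid because the control was exposed to obicetrapib.

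**Search for a correcting passage**

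The rationale in SAP 3.2.3 discusses only obicetrapib levels in earlier studies, which hints at an active-arm rule but does not state one. Protocol 8.7 ("Blood samples for PK assessment will be collected as indicated in Appendix A") and its Appendix A do not separate the arms. Uniform sampling is expected in a blinded trial and does not settle the scope of the criterion either way.

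**The case against.** The strongest reply is that the intent is plain. The population is called On-Treatment, its rationale is about obicetrapib levels, and the analysis repeated in it presupposes a control arm. A sensible programmer would apply the threshold to the obicetrapib arms only, and the separate programming specifications announced in SAP 6 may already say so. A literal run would produce an empty placebo column, which someone would notice. The set is supportive, and no alpha or sample-size figure depends on it.

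Most of this is fair. The omission is probably a drafting slip, and it is unlikely to produce a wrong conclusion unnoticed. The scenario of a misdosed placebo participant has no documented probability and should carry little weight. SAP 3.3.3 already tabulates the number in each analysis population by treatment, so only a breakdown by reason would be new.

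Two things remain. The SAP is the document that fixes membership in advance, and any workable program must depart from its text. And the text leaves open what to do with a placebo participant who has measurable drug. That choice should not be made once concentrations, which themselves reveal allocation, have been seen. SAP 3.2.4 requires the PP Population to be final before unblinding; SAP 3.2.3 has no such safeguard.

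**Conclusion.** The concern holds. As written, SAP 3.2.3 leaves no validly dosed placebo participant in the mITT On-Treatment Population, and 0 of the 3 intended Day 56 contrasts can be estimated unless someone randomized to placebo took obicetrapib. This rests on the literal text and on the inference that placebo-only dosing gives no level above 100 ng/mL.

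The reach is narrow: 1 of the 3 supportive repeats of the primary analysis, the placebo column of the SAP 3.3.4 baseline table for this set, and the placebo count for it in the SAP 3.3.3 table. The mITT primary analysis, the fixed-sequence test, the ITT and PP repeats and the three sensitivity analyses, all run on mITT, are unaffected. It should be fixed, but it does not threaten the trial's main conclusion.

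**What to change.** Before unblinding, amend SAP 3.2.3 in two sentences:

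1. The concentration criterion applies only to participants randomized to obicetrapib; placebo participants need Baseline and Day 56 LDL-C.
2. How a placebo participant with Day 56 obicetrapib above 100 ng/mL is handled.

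Add one row to the SAP 3.3.3 populations table giving, for each obicetrapib arm, the number excluded by the concentration criterion. This matters because the corrected rule still filters the active arms alone on a post-randomization measurement. The amendment restores the control arm but does not remove that selection, and readers need to see how many were dropped at each dose.

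No new data, samples or analyses are needed.

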3.2.4 Per-Protocol (PP) Population

The Per-Protocol (PP) Population will include all participants in the mITT Population who have a Baseline value for the LDL-C assessment, have a Day 56 value for the LDL-C assessment, and who do not experience a major protocol deviation that would potentially impact the primary efficacy endpoint. Major protocol deviations will be defined in the Protocol Deviation Plan within the trial master file to align with International Conference on Harmonization guidelines. The PP Population, along with the reason for exclusion, will be finalized prior to study unblinding. The PP Population will be a secondary population for analysis of the primary efficacy endpoint.

3.2.5 PK Population

The PK Population will include all participants in the mITT Population who have sufficient blood samples collected for valid estimation of PK parameters.

3.2.6 Safety Population

The Safety Population will include all participants who receive at least 1 dose of any study drug. Treatment classification will be based on the actual treatment received. The Safety Population will be the primary population used for the safety analyses.

3.3 Subject Data and Study Conduct

3.3.1 Subject Disposition

Subject disposition will be presented for ITT Population. Counts and percentages of participants who are randomized, complete the study, complete the treatment, prematurely discontinue from the study, reasons for study discontinuation, and primary reason for early termination was due to COVID-19 will be summarized by treatment and overall. For each scheduled visit, counts and percentages of participants who do not complete the visit, partially complete the visit in-person, or complete the visit virtually will be summarized by treatment. The denominator for calculating percentages will be based on the number of randomized participants.

Data listings for subject disposition and exclusion and inclusion criteria violations will be provided.

3.3.2 *Protocol Deviations*

Protocol deviations will be identified based on the clinical data as defined in the Protocol Deviation Plan. The Protocol Deviation Plan will define all protocol deviations as either CSR reportable or non-CSR reportable deviations. Counts and percentages of participants with CSR reportable protocol deviations by deviation category will be summarized by treatment and in total based on ITT Population. A listing of CSR-reportable protocol deviations will be generated.

3.3.3 *Analysis Populations*

Counts and percentages of participants in each analysis population will be summarized by treatment and in total based on ITT Population. Reasons for exclusion from PP Population will also be summarized.

3.3.4 *Demographic and Baseline Characteristics*

The following demographic and baseline characteristics will be summarized:

- Age (years) and age categories (<65 years, 65-75 years)
- Sex
- Childbearing potential
- Race
- Ethnicity
- Height (cm)
- Weight (kg)
- Body mass index (BMI) (kg/m²) and BMI categories (<30 kg/m², ≥30 kg/m²)
- Stratification group (LDL-C value ≥100 or <100 mg/dL)
- Current statin therapy (Atorvastatin 10 mg, 20mg/day, Rosuvastatin 5, 10 mg/day)

Demographic and baseline characteristics will be summarized with descriptive statistics or counts and percentages of participants as appropriate by treatment and in total for the mITT Population and each of the ITT Population, the PP Population, the mITT On-Treatment Population and the Safety Population if they differ from the mITT.

3.3.5 *Medical History*

Medical history will be coded to system organ class and preferred term using the Medical Dictionary for Regulatory Activities (MedDRA) with the version specified in Data Management Plan. Counts and percentages of participants with medical history by system organ class and preferred term will be summarized by treatment and in total based on ITT Population.

3.3.6 *Prior and Concomitant Medications*

Medication start and stop dates that are recorded on the Prior & Concomitant Medications case report form will be used to determine whether the medications are prior or concomitant to the study treatment. Concomitant medications are defined as those used on or after the first dose of study treatment. Prior medications are defined as those used prior to and stopped before the first dose of study treatment. All prior and concomitant medication verbatim terms will be coded using the World Health Organization (WHO) Drug Dictionary with the version specified in Data Management Plan. The numbers and percentages of participants taking prior and concomitant medications in each treatment and in total will be summarized by anatomical therapeutic chemical (ATC) class and preferred term for the Safety Population.

